9.9 Days 1, 2, and 3 Measurements

If not obtained as part of clinical care, patients will have platelets, serum creatinine, total bilirubin, and alanine aminotransferase (ALT) measured on day 3 (+/- 1 day) after administration of the study product.

Arterial blood gases will be obtained at baseline and at hours 6, 12, 18, 24, 30, and 36 (+/- 1 hour for all timepoints) after the initiation of the study product infusion in order to assess the primary endpoint of oxygenation index. Subsequently, arterial blood gases will be obtained on days 2 (48 hours +/- 4 hours) and day 3 (anytime). In the unusual circumstance that a patient does not have an arterial line for ABG monitoring on day 3, the ABG will not be obtained for study purposes alone. If an arterial blood gas is collected +/- 1 hour of an indicated timepoint for clinical purposes, another arterial blood gas does not need to be collected for research.

9.10 Day 7 Measurements

Arterial blood gases will be obtained anytime on days 7 if patient still has arterial line. If not obtained within the past 24 hours as part of clinical care, patients will have platelets, serum creatinine, total bilirubin and alanine aminotransferase (ALT) measured on day 7 (+/- 1 day) after administration of the study product if they are still hospitalized.

9.11 Day 28 Measurements

Patients will be followed daily for adverse events through day 28 after study product administration, death or hospital discharge, whichever occurs first. If a patient is discharged from hospital before day 28, investigators will follow-up by phone interview with the patient, family member or caregiver after day 28 to ensure that no adverse events have occurred through day 28. Mechanical ventilation history (on or off ventilator support), ICU history and the need for dialysis through day 28 after study product administration will also be collected. Decisions about hospital discharge will not be made by study personnel; rather such decisions will be made by clinicians caring for the study subject based on the underlying condition that led to the hospitalization. Also, we will assess neurologic status by the 6 point Glasgow Outcome Score at hospital discharge.

9.12 Day 60 Measurements

Vital status and the need for dialysis will be collected at day 60 after study product infusion. If patients are discharged from the hospital prior to day 60, we will collect this data through telephone interviews with care-givers at the outside facility, or family members, or the patient.

9.13 Post-hospitalization Follow-up

Hospital mortality and discharge location will be collected if patient is discharged from hospital alive after study enrollment. Also, vital status at 6 month after study enrollment will be collected via a structured telephone interview.

10 Data Collection

10.1 Medical History

To be collected from patient charts and patient/surrogate, where applicable.

1. Demographic and admission data
2. Pertinent medical history with comorbidities and physical examination
3. Height, gender, measured body weight, calculated predicted body weight
4. Pre-hospital times and interventions
5. Time on ventilator prior to enrollment
6. High flow nasal oxygen (HFNO) and non-invasive ventilation (NIV) use for the 3 calendar days prior to meeting ARDS criteria
7. Mechanisms of Injury if the primary cause of ARDS due to trauma:
 - a. Abbreviated injury score by region
 - b. Injury severity score
 - c. Presence of hypotension on admission (SBP < 90 within 24 hours of admission)
 - d. Need for blood transfusion, as well as volume of blood and components transfused during the 1st 24 hours after injury.
 - e. Volume of crystalloid resuscitation transfused during the 1st 24 hours after injury.
 - f. Procedures performed prior to randomization
 - g. Intubated on arrival or time to intubation after admission
 - h. Base deficit (lowest level in each 24 hour period)
8. Acute or chronic renal failure and use of dialysis
9. History of lung disease
10. History of solid organ transplant
11. History of bone marrow transplant
12. COVID-19 vaccination status prior to enrollment (number, type, and date of doses)
13. Etiology of ARDS
14. Outpatient medications

10.2 Baseline Assessments

The following information will be recorded during the 24-hour interval preceding randomization. If more than one value is available for this 24-hour period, the value closest to the time of randomization will be recorded. If no values are available from the 24 hours prior to randomization, then values will be measured post randomization but prior to initiation of study drug.

10.2.1 To Be Collected From Patient Charts

1. APACHE III Score
2. Vital signs: Heart rate, systolic and diastolic blood pressure, body temperature, mean arterial pressure, central venous pressure (if available)
3. Ventilator mode, tidal volume, FiO₂ and PEEP, inspiratory plateau pressure, and mean airway pressures. If on a pressure-targeted mode, peak pressure during inspiration will be assumed to be the plateau pressure
4. Arterial PaO₂, PaCO₂, pH and transcutaneous oxygen saturation and base deficit
5. Date and time of all creatinine determinations in the 96 hours prior to enrollment.
6. Frontal chest radiograph – radiographic lung injury score (# of quadrants)
7. Vasopressors or inotropes (epinephrine, norepinephrine, phenylephrine, vasopressin, dopamine > 5 µg/kg/min, dobutamine, phosphodiesterase inhibitors)
8. Suspected or known site of infection
9. Baseline platelet count and kidney/liver function tests: creatinine, total bilirubin, alanine aminotransferase. Make laboratory measurements as specified in Study Procedures **Section 9.3** if not available from testing obtained as part of clinical care
10. Baseline assessments must include all data needed for the 4-point acute lung injury score, SOFA score, Ordinal Scale of Clinical Assessment (OSCI) and trauma registry index (if applicable)
11. COVID-19 test results (if applicable)

10.3 Assessment after Enrollment: Determination of Stable Baseline for Study Product Administration and Monitoring During and After Infusion Protocol

The following parameters will be measured and recorded every 15 minutes for the two hour period used to establish the stable baseline prior to the study product infusion:

1. Respiratory: FiO₂, PEEP, transcutaneous oxygen saturation; additional ventilator parameters will be recorded if clinically available.
2. Cardiovascular: Heart rate, systolic and diastolic blood pressure, vasopressor doses.

The same clinical parameters will be recorded every 15 minutes for the duration of the infusion and every hour for the next 5 hours.

An arterial blood gas will be obtained within 90 minutes prior to beginning the baseline stability period, at the end of the study product infusion (~1 hour), and 6 hours (+/- 1 hour) after the initiation of the study product infusion; additional blood gases will be recorded at 12, 18, 24, 30

and 36 hours (+/- 1 hour for all timepoints) after the initiation of the study product infusion. If an arterial blood gas is collected +/- 1 hour of an indicated timepoint for clinical purposes, another arterial blood gas does not need to be collected for research.

10.4 Assessment after Enrollment: Reference Measurements

The following data will provide the basis for assessing protocol compliance and safety as well as between-group differences in several efficacy variables. Data for each of the variables will be recorded on the days shown in the Time-Events Schedule (**Appendix A**) or until death, discharge from the ICU, or unassisted ventilation for 48 hours.

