- Superficial incisional/wound infections during the 14 days after enrollment.
- Deep incisional wound infections during the 14 days after enrollment.
- Organ (such as lung, liver) or space (such as peritoneum or pleural) infections during the 14 days after enrollment.
- Ventilator associated pneumonia (VAP) during the 14 days after enrollment.

3. Systemic Illness: Systemic illness efficacy endpoints will include:

- Mean SOFA score (127) at days 3, and 7.
- In hospital mortality at 14 days, 28 days, and 60 days.
- Additional prognostic value of neutrophil:lymphocyte ratio.
- Ordinal Scale for Clinical Improvement (OSCI) at days 7, 14 and 28.

To assess organ failure, we will measure serum creatinine (renal function), bilirubin (hepatic function), and platelet count (hematology) at days 0, 3, and 7.

4. Neurologic: Neurocognitive efficacy endpoints will include:

- Neurocognitive function at hospital discharge by the Glasgow Outcome Score (6 points)

5. Thromboembolic: Thromboembolic safety endpoints will include:

- Incidence of thromboembolic events: Measured by ultrasound of the deep venous system or CT-angiography of the chest when clinically indicated.
- Additional prognostic value of fibrinogen at baseline.

6. Biologic: Biomarker analysis will include: Changes in levels of plasma, urine, and genetic biomarkers at baseline compared to 6, 24, 48, and 72 hours, including:

- Endothelial injury (angiopoietin-2 [Ang-2])
- Lung epithelial injury (Receptor for Advanced Glycation Endproducts [RAGE])
- Pro-inflammatory markers (interleukin-6, interleukin-8, soluble tumor necrosis factor-1 [sTNF-1], intercellular adhesion molecule-1 [ICAM-1], interferon gamma-induced protein-10 [IP-10], interleukin-10 [IL-10], vascular endothelial growth factor [VEGF], matrix metalloproteinase-8 [MMP-8], thrombomodulin, surfactant protein-D [SP-D], triggering receptor expressed on myeloid cells-1 [TREM-1], interleukin-18 [IL-18], plasminogen activator inhibitor-1 [PAI-1])

- Protein C (marker of impaired coagulation)
- Pro-resolving lipids (lipoxin A4, resolvin D₁)
- Biomarkers that reflect the paracrine activity of the administered hMSCs (angiopoietin-1 [Ang-1], keratinocyte growth factor [KGF])

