10.4.1 Reference Measurements (to be collected from patient charts)

The following parameters will be measured and recorded at the time of Randomization as well as on subsequent dates using values closest in time to 8:00 A.M. on the days specified in the Time-Events Schedule (**Appendix A**). The following conditions will be ensured prior to measurements: no endobronchial suctioning for 10 minutes; no invasive procedures or ventilator changes for 30 minutes. All vascular pressures will be zero-referenced to the mid-axillary line..

1. If receiving assisted ventilation, record daily up to day 7:
 - a. Tidal volume, FiO₂, PEEP, inspiratory plateau pressure, and mean airway pressures
 - b. Pressure during inspiration if on a pressure targeted mode (PSV, PCV, etc)
 - c. Arterial PaO₂, PaCO₂, pH and transcutaneous oxygen saturation
2. Fluid intake and output
3. Vital signs: Heart rate, systolic and diastolic blood pressure, body temperature, CVP
4. Modified Brussels Score data on days 0 through 14
 - a. Vasopressor use (Y/N), lowest systolic blood pressure, creatinine, bilirubin, and platelet count for the day
5. The date and value of the highest creatinine between days 15 and 28
6. Safety laboratory studies: all creatinine and bilirubin measurements will be recorded as above. Creatinine, bilirubin and ALT will be measured and recorded as safety labs on day 7 if not obtained as part of clinical care.
7. Data regarding infections, including:
 - a. Surgical site and wound infections by CDC criteria
 - b. Ventilator associated or nosocomial pneumonia as diagnosed by CDC criteria
 - c. Culture-proven bacteremia
 - d. SARS-CoV-2 virus infection
8. Blood product transfusions
9. On-study procedures and surgical interventions
10. Co-enrollment in randomized clinical trials of other interventions and treatments related to SARS-CoV-2 infection
11. Inpatient medications (selected)
12. Must include all data needed for the 4-point acute lung injury score (including frontal chest radiograph), SOFA score, OSCI score and trauma registry index (if applicable)
13. D-dimer, lymphocyte count, neutrophil count, fibrinogen, ferritin and serum C-reactive protein (if applicable)

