Ventilator history and ICU history [@]																			X	
Need for, timing and duration of dialysis																		X	X	
Vital Status §																		X	X	
Ordinal Scale for Clinical Improvement (OSCI)	X														X			X	X	
Incidence of barotrauma		X						X	X	X				X						

X=Required; A=When available; ~Data gathered on days 0-14 or until d/c from study hospital; \$=Data recorded every 15 minutes for at least two hours during "stable baseline" period and until the initiation of study product infusion, every 15 minutes for the duration of the infusion and every hour until 6 hours, then 12, 24 and 48 hour from the initiation of study product infusion; #Data recorded every 15 minutes for at least two hours during "stable baseline" period and until the initiation of study product infusion, every 15 minutes for the duration of the infusion and every hour until 6 hours, then 12, 18, 24 and 36 hour from the initiation of study drug infusion, then day 2, 3, 4, 5, 6, and 7; &=ABG mandatory at the following timepoints: within 6 hours of randomization, prior to the start of the infusion (within 90 minutes of starting the baseline stability period); within 15 minutes of the end of MSC infusion (~1 hour); after the initiation of the study product infusion, ABGs will also be REQUIRED at 6, 12, 18, 24, 30, 36 hours (+/- 1 hour for all timepoints), day 2 (48 hours +/- 4 hours), 3 and 7 (anytime) if patient still has arterial line after study product infusion; €=Record only one episode during the 14 day period after study product infusion, no need for further assessment once first diagnosis is confirmed; %=Labs not available in the 24 hours before randomization must be obtained; ¶=Data gathered for first 14 days during current hospital admission; @=Measure at day 28. The 28-day follow up will be a telephone interview with structured survey if patient discharged prior to day 28; §=Measure at day 28, day 60, hospital discharge alive, and 6 months; the 6 month follow up will be a telephone interview with structured survey. B=Patient must achieve a stable baseline for ≥ 2 hours and the administration of study product must be initiated within 14 days of initial ICU admission; C=Record available clinical data within 24 hours prior to study randomization; D=Record ECHO if available. If more than one ECHO data available, select the data closest to randomization; E=Record clinically available worst SBP, PaO2/FiO2, SpO2/FiO2, creatinine, platelets, bilirubin, and vasoressor use; F=Measured on day 0, 1, 2, 3, 7 when patient is on assisted breathing; G=Record clinically available creatinine in the 96 hours prior to randomization, the worst creatinine of the day from day 1-14, the date and value of the highest creatinine between days 15-28 and the lowest value during the entire hospitalization obtained off dialysis; H=Data required prior to randomization, day 3 (+/-1 day) and day 7 (+/-1 day); J=Mandatory at the following timepoints: pre-randomization, pre-infusion, day 1, 2, 3, 7, 14 and the date of hospital discharge; K=Record outpatient medication (anticoagulants/antiplatelets/antifibrinolytic) within 7 days prior to current hospital admission; record the following medication and procedures (glucocorticoids, NMBD, inhaled vasodilators, prone positioning, recruitment maneuvers, ECMO) prior to randomization and on day 1-7; and inpatient trauma specific medications for first 14 days during current hospital admission; M= Record any co-enrollment of clinical trials and COVID-19 related therapies within 7 days prior to current hospitalization until hospital discharge; N=Blood specimens are required before the study product infusion, at 6, 12, 24 hours (+/- 1 hour), and 2 (48 hours +/- 4 hours), 3 days (anytime) after the initiation of the study product infusion. O=Urine specimens are required before the study product infusion, at 24 hours and 2 days (48 hours +/- 4 hours) after the initiation of the study product infusion.

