12.7.2 Secondary Infection endpoints

Superficial incisional/wound infections, deep incisional wound infections, and organ/space infections, and ventilator associated pneumonia during the 14 days after study product administration by individual patient, as well as the allocated group and the time of events will be

listed. Also, the above infection endpoints will be summarized as patient counts and percentages by allocated group in modified ITT Population.

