12.7.8 Thromboembolic events

Thromboembolic events after study product administration will be listed by individual patient, with their allocated treatment and the occurring time of thromboembolic events, and will be summarized as patient counts and percentages by allocated group in modified ITT Population, and analyzed by Pearson's chi-square tests or Fisher exact tests, as appropriate.

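### The rule ending reference data collection at ICU discharge or 48 hours off the ventilator contradicts the 14-day infection window, and the thromboembolic footnote conflicts with its own study-day row

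*Protocol*

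**What the plan says.** **Infection**

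- Protocol 10.4, repeated in SAP 6.1.4, governs the reference measurements. Data for each variable are recorded on the days in the time-events schedule "or until death, discharge from the ICU, or unassisted ventilation for 48 hours". No item is exempted.
- Item 7 of the list that follows (Protocol 10.4.1) holds the infection data: surgical site and wound infections, "Ventilator associated or nosocomial pneumonia as diagnosed by CDC criteria", bacteremia and SARS-CoV-2 infection.
- Protocol 6.2.1 defines the endpoints over 14 days, for example "Superficial incisional/wound infections during the 14 days after enrollment" and "Ventilator associated pneumonia (VAP) during the 14 days after enrollment".
- The schedule footnote for infections (Protocol Appendix A, SAP Table 2) reads "Record only one episode during the 14 day period after study product infusion". It ends at the first diagnosis and has no ICU or ventilator stop.
- SAP 12.7.2 analyses "ventilator associated pneumonia during the 14 days after study product administration by individual patient". It therefore counts from infusion, where Protocol 6.2.1 counts from enrollment.

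**Thromboembolic events**

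- The footnote shared by thromboembolic complications, positive blood cultures and DVT prophylaxis reads "Data gathered for first 14 days during current hospital admission". The rows themselves are marked by study day through day 14.
- Protocol 6.2.1 labels thromboembolic events a safety endpoint and gives no length of follow-up. SAP 12.7.8 says only "Thromboembolic events after study product administration will be listed by individual patient".

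**The concern.** The 10.4 stop is triggered by leaving the ICU or by staying off the ventilator, which are outcomes the treatment is meant to improve. If it is applied to infections, the length of surveillance depends on recovery. An arm that recovers faster is watched for fewer days and records fewer infections even with no true effect, and that would read as a benefit in a named secondary efficacy category.

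Nothing downstream would correct this. SAP 12.7.1 uses logistic regression for infection and SAP 12.7.2 uses patient counts and percentages, so time at risk does not enter. SAP section 9 applies no imputation unless indicated, and none is indicated here. Adverse-event follow-up to day 28 is not a dependable backup: Protocol 6.2.2 and 12.2 class nosocomial infections as expected events, not reportable unless judged study-related or unexpectedly severe or frequent.

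For thromboembolic events the ICU/48-hour stop is not the issue, because they are not in the 10.4.1 list. The trouble is an undefined window and a footnote that, read literally, counts from hospital admission. Infusion may begin up to 14 days after initial ICU admission (Protocol 7.3, criterion 4).

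**Working it through.** The plan states no figure on this point, so there is none to reproduce. The check is of windows, followed by an illustration under stated assumptions.

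**1. Infection window under each rule**

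- If the footnote and SAP 12.7.2 govern, 14 of 14 days are observed in every surviving patient who remains in hospital.
- If the 10.4 stop governs, days observed = min(14, stop day). Appendix D allows the first weaning assessment 24 hours after enrollment. Adding 48 hours unassisted puts the earliest stop by that route at about day 3: 14 − 3 = 11 days lost (79%). A day-7 stop loses 7 days (50%) and a day-10 stop loses 4 (29%).

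**2. What differential stopping could do**

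Assumptions, none from the documents: no treatment effect, a constant hazard of 1.5% per day in both arms, and recording stopped at day 7 in 30% of the faster-improving arm and 15% of the other.

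- 14-day risk: 1 − exp(−0.015 × 14) = 18.94%
- Recorded risk in a patient stopped at day 7: 1 − exp(−0.015 × 7) = 9.97%
- Faster arm: 0.70 × 18.94 + 0.30 × 9.97 = 16.2%
- Other arm: 0.85 × 18.94 + 0.15 × 9.97 = 17.6%
- False benefit: (0.30 − 0.15) × (18.94 − 9.97) = 1.3 points (1.346 before the risks are rounded), or 0.01346 × 60 = 0.8 of a patient per arm

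Range: take 14-day risks R of 10% to 30%, stop days of 3 to 10, and stopped shares of 40% v 25% or 50% v 30%. With hazard −ln(1 − R)/14, the false benefit runs from 0.4 points (R = 10%, day 10, 40% v 25%) to 4.5 points (R = 30%, day 3, 50% v 30%), a risk ratio of 0.96 to 0.80. In every case it favours the arm that stops sooner. The constant hazard is generous to the concern: if infection risk falls after ICU discharge, the bias is smaller.

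**3. Thromboembolic window, footnote read literally**

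Post-infusion days = max(0, 14 − hospital day of infusion).

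| Infusion on hospital day | Post-infusion days |
|---|---|
| 3 | 11 |
| 7 | 7 |
| 10 | 4 |
| 14 | 0 |

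The row marks, by contrast, imply 14 days for everyone still in hospital. The marks were read from SAP Table 2, where the grid is legible.

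**The case against.** The best reply is that the specific rule should override the general one. The infection footnote, the infection row in SAP Table 2 and SAP 12.7.2 all point to 14 days after infusion. The 10.4.1 list also asks for organ-dysfunction data to day 14 and the highest creatinine between days 15 and 28, which could not be collected if the stop applied to every item. This stands in part: a reader might infer that infection data definitely stop at ICU discharge, and the documents do not establish that. What they show is an unresolved contradiction. That some items must be exempt is a reason to name them, because a coordinator following 10.4 as written would stop. Protocol 10.5, the separate list of endpoint determinations, does not include infections and so does not settle it.

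Three further readings go too far.

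- A reader might infer that the ordinal scale for clinical improvement is truncated, since its data are item 12 of the same list. It is not: SAP 8.7 collects it for all patients at days 0, 7, 14 and 28 by chart review or telephone, and Protocol 10.5 lists it separately.
- A reader might infer that a stated thromboembolic window is cut short. No fixed window is stated, and the footnote could also mean the first 14 study days while in hospital. The defect is ambiguity and a missing end day.
- A reader might expect heavy loss of ventilator-associated pneumonia. That loss is largely limited to patients re-ventilated after the stop; wound and organ/space infections are more exposed.

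It is also fair that SAP 12.5 treats secondary endpoints as supportive and exploratory, that the assumed effect is small, and that late infusion also requires ARDS criteria first met within the previous 72 hours.

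**Conclusion.** The point holds as a conflict between collection rules, not as proof that data are truncated. For infection, two incompatible rules stand in both documents with no order of precedence. One of them ties surveillance to recovery, and the analysis has no means of noticing. If sites follow it, the bias favours whichever arm improves faster: about 1.3 points in the illustration and 0.4 to 4.5 points over the ranges tried. All infection and stopping rates are assumptions, and the direction also assumes that one arm does leave the ventilator or ICU sooner. For thromboembolic events, the window has no stated end and the footnote disagrees with its row. Only the literal reading loses post-infusion days, and the documents do not say how many patients would be infused late. The primary endpoint is not affected. The correction is worth making because the ambiguity touches a secondary efficacy category and a safety endpoint and is cheap to remove.

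**What to change.** - In Protocol 10.4 and SAP 6.1.4, exempt the infection items from the ICU-discharge and 48-hour stop. Record them through day 14 after infusion whatever the ICU or ventilator status, and record the date of any earlier hospital discharge so that incomplete observation is visible.
- Use one anchor, enrollment or infusion, in both Protocol 6.2.1 and SAP 12.7.2.
- Reword the footnote for thromboembolic complications and positive blood cultures in Appendix A and SAP Table 2 to study days 0 to 14 relative to infusion. State the same window for thromboembolic events in Protocol 6.2.1 and SAP 12.7.8.

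The cost is a few wording changes in each document and modest extra chart abstraction for patients on the ward. The schedule already marks these rows to day 14, so no new visit or test is needed.
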